Determine the impact of upper airway stimulation on peripheral arterial tonometry ratio related to obstructive episodes in this cohort of patients with moderate-severe obstructive sleep apnea

Hypothesis: The peripheral arterial tonometry ratio related to obstructive episodes will be improved with increasing levels of upper airway stimulation

Aim 2a

Determine the impact of upper airway stimulation on flow mediated dilation in this cohort of patients with moderate-severe obstructive sleep apnea

Hypothesis: The flow mediated dilation parameters will be improved at therapeutic levels of upper airway stimulation and returned to pre-operative levels after 30-day withdrawal period

Aim 2b

Determine the impact of upper airway stimulation on peripheral arterial stiffness in this cohort of patients with moderate-severe obstructive sleep apnea

Hypothesis: The peripheral arterial stiffness parameters will be improved at therapeutic levels of upper airway stimulation and returned to pre-operative levels after 30-day withdrawal period

Aim 2c

Determine the impact of upper airway stimulation on 24-hour ambulatory blood pressure in this cohort of patients with moderate-severe obstructive sleep apnea

Hypothesis: The 24-hour ambulatory blood pressure will be improved at therapeutic levels of upper airway stimulation and returned to pre-operative levels after 30-day withdrawal period

Aim 2d

Determine the impact of upper airway stimulation on serum biomarker profile in this cohort of patients with moderate-severe obstructive sleep apnea

Hypothesis: The serum biomarker profile will be improved at therapeutic levels of upper airway stimulation and returned to pre-operative levels after 30-day withdrawal period

6. Study Design and Methods

Each participant will undergo three sets of blood testing. Each set of testing will require travel to the Emory Clinical Cardiovascular Research Institute (ECCRI) facility at Woodruff Memorial Research Building on Clifton Campus. The subjects will be provided directions, lunch and parking vouchers for each visit. The subject will be registered at the EECRI facility each time and undergo fasting bloodwork.

Study Timeline

- Post-operative appointment: obtain consent for study enrollment (Day 1)
- WatchPAT baseline home sleep test (Night 1)
- Baseline 24-hour ambulatory blood pressure monitoring (Day 2-3)
- Baseline serum biomarkers/vascular testing (Day 15)
- Device Activation (Day 15)
- In-lab Polysomnography Titration (Day 45)

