This study is designed to learn more about the cardiovascular improvement with this form of treatment of obstructive sleep apnea. The study results may be used to help others in the future.

Information to be Collected

- Medical information about you including your medical history and present/past medications.
- Results of exams, procedures and tests you have before and during the study.

Specimens to be Collected

- Blood samples (before, during and after sleep apnea treatment)

Randomization and Blinding

There will be no randomization. Interpretation of all tests (sleep tests, ambulatory blood pressure monitoring, vascular test and blood tests) will single-blinded.

7. Data Sample Information

We will obtain a blood sample (about 1/2 cup) from you and store the blood for future analysis. The blood sample may be obtained by a nurse or physician as part of other blood draws you are undergoing during your visit(s). A study ID number will be used to link your blood sample to your other information. The DNA (genetic material) in your blood sample will be isolated and stored for future studies. Permanent cells may be created. Once DNA is isolated, it can be duplicated indefinitely for future research. Serum and plasma from your blood samples will also be stored and analyzed for a variety of biochemical factors. If you are less than 60 years old an extra tube of blood (about 1/2 tablespoon) will be collected. This extra tube of blood will be used to look at a special type of cell in your blood. This type of blood cell may help explain the difference between young women and young men with heart disease.

8. Community Participation

Not applicable

9. Participant Selection

Requested sample size: 50 subjects

Expected refusal/withdrawal: 10 subjects

Subjects completing study: 40 subjects

Inclusion criteria: All patients are English-speaking, greater than 18 years old and able to give informed consent. HGNS inclusion criteria per FDA require an AHI ≥ 20 on recent sleep testing, unable to use positive airway pressure therapy, BMI < 32 , without circumferential collapse on drug-induced sedated endoscopy. In essence, the inclusion criteria are those patients who have undergone HGNS implantation.

Exclusion criteria: active smokers, unstable and untreated coronary or peripheral artery disease, alpha-blockers, severe and inadequately controlled arterial hypertension.

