also be provided lunch and parking vouchers for each time (3 in total) that he/she undergoes cardiovascular testing. The subject will not be responsible to pay for any cardiovascular testing as this is being done outside routine clinical care.

13. Statistical Analysis

With 40 subjects, we will have 89% power to detect a difference of 0.1 in the PAT ratio (primary outcome) with a standard deviation of 0.2 and alpha of 0.05.

Each subject will have a baseline PAT ratio derived from the average of the 10 obstructive events without stimulation (Aim 1). The PAT ratios at each stimulation level (5-7 stimulation levels based on previous experience) will be averaged from 5 obstructive events at each level. With greater than 30 data points per individual, linear regression will be performed for each subject with stimulation level as the main effect variable and PAT ratio as the outcome variable. We will determine if stimulation level is positively associated with PAT ratio. We will also perform linear regression, in a similar manner, from the combined values of the cohort to determine an effect at the sample level.

An interim analysis will not be performed as the primary outcome variable is largely observational (non-interventional); thus, the findings are expected during the treatment of moderate-severe obstructive sleep apnea

14. Data Safety and Monitoring Board

A DSMB will not be required. Access to this database will be restricted by a database manager and will be password protected. The only individuals who will be able to see patient identifiers, like name, address, and social security number, will be the Principal Investigator, research coordinators, recruiters and the database managers. Other investigators will have different passwords that will provide restricted access to the database. Those with restricted access will be able to query the database for scientific information/variables, but will not be able to view information on patient identifiers such as name, address, and social security number. If investigators with restricted access want to conduct studies which require them to obtain patient identifiers so that patients can be contacted for follow-up information/follow-up visits, these investigators will have to submit a separate protocol to IRB to get permission to obtain patient identifiers and contact patients.

15. Confidentiality

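### The Aim 1 cohort slope pools subjects with 5 to 7 levels on an undefined level scale, weights them unequally, and has no stated link to the 0.1 difference the study is sized on

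*Combined protocol and SAP*

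**What the plan says.** The Aim 1 hypothesis (Section 5) is that "The peripheral arterial tonometry ratio related to obstructive episodes will be improved with increasing levels of upper airway stimulation". Section 13 takes a baseline from 10 obstructive events with stimulation off. For the levels it says: "The PAT ratios at each stimulation level (5-7 stimulation levels based on previous experience) will be averaged from 5 obstructive events at each level". For each subject, "linear regression will be performed for each subject with stimulation level as the main effect variable and PAT ratio as the outcome variable". The next steps are to see whether the association is positive, and to run the same kind of regression on the whole cohort's values together for a sample-level effect.

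No section states the unit of level, the size of a step, why the number of levels varies, or whether the cohort regression contains a subject term. The zero point is defined implicitly by the events with stimulation off.

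The sample size statement in Section 13 is on another scale. With 40 subjects, "we will have 89% power" for a difference of 0.1 in the PAT ratio, which is named as the primary outcome, "with a standard deviation of 0.2 and alpha of 0.05". It does not name the two conditions that differ. The cohort is single-arm: "There will be no randomization".

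**The concern.** The within-subject regression does no harm by itself: rescaling level does not alter the sign or p-value of a subject's own slope. The difficulty begins when all subjects' values go on one axis.

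- **Weight.** Least squares weights a subject by the spread of that subject's levels, so a longer range counts for more.
- **Support.** With step-number coding, only some subjects supply data at levels 6 and 7. Without a subject term, differences between subjects then enter the slope.
- **Units.** The result is PAT ratio per level. The study is sized on a total change, and nothing in the plan converts one into the other.

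This is the only cohort-level analysis described for the primary outcome. Two analysts could follow Section 13, code level differently, and report cohort effects that cannot be compared with each other or with 0.1.

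**Working it through.** **Inputs from Section 13:** 40 subjects, difference 0.1, SD 0.2, alpha 0.05, power 89%, 10 events off stimulation, 5 events per level, 5 to 7 levels.

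**Assumptions:** two-sided test; levels coded 0 (off), 1, ..., k; single events as data points (10 + 5k = 35, 40 or 45, consistent with the plan's count of more than 30 per person); noise-free straight lines from a common baseline.

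**1. The plan's own figure.** One difference per subject, normal approximation: 0.1 / (0.2/√40) = 3.162, and power = Φ(3.162 − 1.960) = 88.5%, which agrees with 89%. The paired t version gives 86.9%. So the stated power fits a test of one change per subject. It is not the power of a pooled slope.

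**2. Weight per subject.** Sxx = Σx² − (Σx)²/n.

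- k = 5: 275 − 75²/35 = 114.3
- k = 6: 455 − 105²/40 = 179.4
- k = 7: 700 − 140²/45 = 264.4

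The ratio of 7 levels to 5 is 264.4/114.3 = 2.3 within subjects. It is 2.4 if level means are used (42/17.5), and about 2.2 if deviations are taken from the pooled mean. With equal thirds at 5, 6 and 7 levels, the 7-level third supplies 264.4/558.1 = 47% of the within-subject weight: the largest share, but not a majority.

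**3. Pooled slope without a subject term, half the subjects at 5 levels and half at 7.** Let c5 and c7 be the off-to-top changes. For one subject of each kind, n = 80, Σx = 215 and Σx² = 975.

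- Sxx = 975 − 215²/80 = 397.19
- Sxy = (55c5 + 100c7) − (215/80)(15c5 + 20c7) = 14.69c5 + 46.25c7

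The true mean change is 0.10 in every row:

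| c5 | c7 | Pooled slope per step | Over 6 steps | Mean of slope × own range |
|---|---|---|---|---|
| 0.15 | 0.05 | 4.516/397.19 = 0.0114 | 0.068 | 0.10 |
| 0.10 | 0.10 | 6.094/397.19 = 0.0153 | 0.092 | 0.10 |
| 0.05 | 0.15 | 7.672/397.19 = 0.0193 | 0.116 | 0.10 |

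The extreme slopes differ by 0.0193/0.0114 = 1.7 times.

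**4. Adding a subject intercept.** Slope = (114.3·c5/5 + 264.4·c7/7)/378.7, which gives 0.0140, 0.0160 and 0.0180 per step, or 0.084, 0.096 and 0.108 over 6 steps. The spread shrinks but remains. In the equal-change case, 0.0160 reads as 0.080, 0.096 or 0.112 when converted with 5, 6 or 7 steps.

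**5. Sensitivity to linearity.** Suppose the whole 0.10 change comes at the top step. The subject slope is then 5 × 0.1 × (k − mean x)/Sxx.

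- k = 5: 0.5 × 2.857/114.3 = 0.0125, and times 5 = 0.0625
- k = 7: 0.5 × 3.889/264.4 = 0.00735, and times 7 = 0.051

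The subject's mean at the highest level minus baseline gives 0.10 in both cases.

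**The case against.** The best defence is that Section 13 is silent on the scale, and silence does not show that levels lack a common one. A reader might infer that steps cannot be compared between subjects, but the documents do not say so. If level is a device setting in a shared unit, the slope is change per unit and the unequal-steps point falls away. That stands. What remains is that weight then goes to subjects with the widest range, and that a slope per unit still needs a stated range before it can be set against 0.1.

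A reader might also infer that subjects with more levels are those who respond poorly, so that the weighting is informative. The documents give no rule for the number of levels beyond previous experience and no link to response. The rows with unequal changes show what could happen, not what is expected; with equal changes the reading is 0.092.

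Third, Aim 1 asks whether the ratio improves as level rises, and the pooled slope keeps its sign in every case above. The plan does not promise an off-to-top estimate. That is fair as regards direction. But Section 13 also wants a sample-level effect, and it sizes the study on an amount.

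Finally, one might tie the scale to a level chosen at the Day 45 titration. The timeline lists that titration but does not say that Aim 1 levels are tested there or that a level is selected, so the documents do not support that anchor.

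**Conclusion.** The concern holds in a limited form. As written, the cohort regression uses a predictor without a defined unit or coding, weights subjects by the spread of their levels, and yields a slope with no stated conversion to the 0.1 difference. The 2.3-fold weight depends on step-number coding. The readings of 0.068 to 0.116 for a true mean of 0.10 also depend on a half-and-half mix of 5 and 7 levels and on assumed changes, so they are illustrative and not an estimate of bias in this trial. The documents do not establish that no common scale exists, that the weighting is informative, or that the 89% is miscalculated. This is still more than a missing definition, because an analysis that weights subjects equally and matches the form of the power calculation is available from the same data.

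**What to change.** In Section 13:

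1. State the unit and coding of stimulation level, with 0 for events without stimulation, and whether single events or level means are the data points.
2. Replace the pooled cohort regression with the equally weighted mean of the per-subject slopes and a one-sample t interval.
3. For comparison with 0.1, multiply each subject's slope by that subject's own tested range (off to highest level tested). Alternatively, use the subject's mean PAT ratio at the highest level minus baseline, which does not assume linearity. Choose one in advance.
4. Say that the 0.1 and the SD of 0.2 refer to that per-subject change, if they do. The power is then 88.5% (z) or 86.9% (t).

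The cost is a few sentences and no new data. Equal weighting gives up a little precision. With independent events of equal variance σ², slope times range has variance 25σ²/114.3 = 0.219σ² for 5 levels and 49σ²/264.4 = 0.185σ² for 7, so on this scale equal weights are close to optimal. The highest-level difference has variance σ²(1/10 + 1/5) = 0.30σ², which is 1.4 to 1.6 times as much event noise. That is the price of not assuming a straight line.

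### Section 13 is inconsistent about the unit of analysis for Aim 1 and rests the first conclusion on about 40 per-subject regressions with no rule for combining them

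*Combined protocol and SAP*

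**What the plan says.** Section 13 (Statistical Analysis) describes the Aim 1 data in two ways. Each subject's baseline is "derived from the average of the 10 obstructive events without stimulation (Aim 1"). The ratio at each active setting is likewise an average, over 5 events, with "5-7 stimulation levels based on previous experience". On that description a subject contributes one baseline value and 5 to 7 level values.

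The next sentence counts differently. It opens "With greater than 30 data points per individual" and continues that "linear regression will be performed for each subject with stimulation level as the main effect variable and PAT ratio as the outcome variable". The decision statement follows directly: "We will determine if stimulation level is positively associated with PAT ratio". Only after that does the section add a regression on the cohort's combined values, done in a similar way, for an effect at sample level.

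Section 9 (Participant Selection) gives the number of regressions: "Subjects completing study: 40 subjects". Section 13 names no test, threshold, sidedness or multiplicity rule for them. Its only alpha, 0.05, is in the power statement, which assumes an SD of 0.2 and reads in part: "With 40 subjects, we will have 89% power to detect a difference of 0.1 in the PAT ratio (primary outcome").

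**The concern.** There are two linked problems.

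- **Unit of analysis.** Level averages and individual events are different data sets. Events recorded at one setting in one subject may share sleep stage, body position, time of night and sensor state. Ordinary regression on single events treats them as independent; if they are not, the standard error of the slope is too small. Regression on level averages avoids most of this, but then the stated reason for trusting a per-subject fit, a large number of points, no longer applies.
- **Number of determinations.** The first conclusion about the primary outcome is drawn subject by subject, about 40 times. The plan does not say what makes one subject positive, or what pattern across subjects would support Aim 1. Nothing rules out a report that counts subjects with a significant association, and such a count is not zero when stimulation has no effect.

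**Working it through.** **Inputs from the documents.** 40 completers (section 9). From section 13: alpha 0.05, difference 0.1, SD 0.2, stated power 89%, 10 baseline events, 5 to 7 levels, 5 events per level, more than 30 points per subject.

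**Inputs assumed.** Two-sided tests at 0.05 for each subject; within-level correlation (ICC) from 0 to 0.3; normal errors; equally spaced levels with baseline at level 0; independent subjects.

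**1. The plan's own figure.** A two-sided paired z-test gives power = Φ(0.1 / (0.2/√40) − 1.96) = Φ(3.162 − 1.960) = 88.5%, which agrees with the stated 89%; a paired t-test gives 86.9%. The power statement therefore fits a single paired comparison across 40 subjects. It does not describe per-subject regressions.

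**2. Points per subject.**
- Level averages: 1 + 5 = 6 to 1 + 7 = 8.
- Individual events: 10 + 5×5 = 35 to 10 + 7×5 = 45.

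Only the second count exceeds 30, so the two sentences cannot describe the same regression.

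**3. False positives with valid tests.** Under no effect, a two-sided 0.05 test is significant in the positive direction with probability 0.025.
- Expected number: 40 × 0.025 = 1.0.
- P(at least one) = 1 − 0.975^40 = 64%.
- P(at least three) = 8% (binomial).

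If the tests were one-sided at 0.05, the figures would be 2.0 expected, 1 − 0.95^40 = 87%, and 32%.

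**4. False positives if single events are regressed.** This is a simulation under no effect (40,000 subjects per scenario) of the ordinary slope t-test on 10 baseline events plus 5 events at each of 5, 6 or 7 levels, with a shared random effect per level. Ranges run over 5 to 7 levels.

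| Assumed ICC | Two-sided error per subject | Falsely positive subjects of 40 |
|---|---|---|
| 0 | 5% | 1.0 |
| 0.1 | 12% | 2.4–2.5 |
| 0.2 | 19–20% | 3.8–4.0 |
| 0.3 | 26% | 5.0–5.2 |

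Rounded, these are about 2.4, 3.8 and 5.1 at 0.1, 0.2 and 0.3. At 0.2 the chance of three or more is about 75%; at 0.3 it is about 90%.

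**5. False positives if level averages are regressed.** With unweighted averages the expected number is 0.8 to 1.0 of 40 at every ICC tried. Weighting by number of events gives about 1.0 to 1.3 for ICC 0 to 0.3. It slightly exceeds 1.0 because 10 baseline events carry less than twice the information of 5 when events are correlated. Either way the clustering inflation is essentially removed.

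**The case against.** The strongest reply is that little depends on the per-subject fits. Aim 1 in section 5 is framed for the cohort, and section 13 already plans a regression on the combined cohort values. No p-value or threshold is attached to individual subjects, and nowhere does the plan say that positive subjects will be counted. A few positive subjects beside a null cohort result would hardly support a claim of effect. The averaging sentence can also be taken at its word, and then there is no within-level clustering to ignore.

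Most of this stands as a limit on the point. A reader might infer that several subjects will show a false association even if stimulation does nothing. The documents do not support that: at their only alpha, read two-sided, the expected number is 1 of 40. Three or more as the expected count needs both event-level regression and, for two-sided tests, an ICC somewhere between 0.1 and 0.2, which the documents do not give. A reader might also infer that each subject really carries only 6 to 8 points' worth of information. At an ICC of 0.1 with 6 levels, the usual design effect gives 30/1.4 + 10/1.9 ≈ 27 effective events of 40, far from 7.

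The reply does not remove the defect. The sentence that specifies the per-subject regression relies on a count that only single events can reach. The cohort regression is introduced as an addition and is not named as the sole basis for Aim 1. If averages are intended, the data-point justification is wrong and the 40 results still lack a rule.

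**Conclusion.** The point holds as an internal inconsistency with a missing decision rule. Section 13 gives two incompatible data units (6 to 8 averages, or 35 to 45 events) and draws its first Aim 1 conclusion from about 40 regressions without saying how they combine.

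The size is modest if tests are valid: about 1 falsely positive subject of 40, with a 64% chance of at least one. It becomes material, about 2.4 to 5.1 subjects, only if single events are regressed and the within-level correlation is 0.1 to 0.3. Per-subject testing at two-sided 0.05 is a reading of the text, and the correlation is an assumption. The direct arithmetic is firm; the simulated counts depend on the stated model. This does not show that the cohort-level conclusion would be wrong. The plan should be corrected because the correction costs almost nothing.

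**What to change.** Amend section 13 as follows.

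1. Make the level average the regression unit, weighted by its number of events (10 at baseline, 5 at each active level), and delete the justification based on more than 30 data points.
2. Report the roughly 40 per-subject slopes descriptively, with their spread, and state that no significance claim will be made for any individual.
3. Name one cohort-level test, with the subject as the unit, as the sole basis for the Aim 1 conclusion. Examples are a one-sample test of the slopes or a mixed model with a random slope per subject. State its sidedness and alpha.

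The cost is SAP wording only; no visit, measurement or sample size changes. The downside is that the trial gives up significance claims about individual subjects.

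### The only cohort-level analysis of the primary PAT outcome pools repeated values with no subject term, so its standard error and p-value are not valid, in a direction the plan does not fix

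*Combined protocol and SAP*

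**What the plan says.** Section 5, Aim 1, states the hypothesis: "The peripheral arterial tonometry ratio related to obstructive episodes will be improved with increasing levels of upper airway stimulation". Section 13 makes the PAT ratio the primary outcome and gives the planned power: "With 40 subjects, we will have 89% power to detect a difference of 0.1 in the PAT ratio (primary outcome"). The calculation takes the SD as 0.2 and alpha as 0.05. It does not say what the standard deviation describes and names no test.

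For the analysis, each subject has a baseline from 10 events without stimulation. The number of levels is given as "5-7 stimulation levels based on previous experience", and the PAT ratios "will be averaged from 5 obstructive events at each level". The section continues: "With greater than 30 data points per individual, linear regression will be performed for each subject", with level as predictor and PAT ratio as outcome. For the cohort it plans "linear regression, in a similar manner, from the combined values of the cohort to determine an effect at the sample level".

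The document mentions no subject effect, mixed model, GEE, robust variance or summary of the per-subject slopes. Section 9 refers to an intention-to-treat analysis but gives no model.

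**The concern.** The values entering the cohort regression come in clusters of one subject each. Subjects differ in their general PAT level and in how strongly they respond to stimulation. Ordinary regression on the combined values ignores both.

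The two sources push in opposite directions. Differences in level go into the residual and make the reported standard error too large. Differences in response make the true uncertainty larger than the regression reports. Which one dominates depends on quantities the plan does not give, and on whether rows are events or averages, which Section 13 leaves open. If subjects have different numbers of levels, differences in PAT level between subjects also leak into the pooled slope.

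The study is single-arm, and the forty separate regressions give no cohort conclusion without a rule for combining them. The primary claim therefore rests on this one regression. It could declare an effect too often or miss a real one, and a reader could not tell which.

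**Working it through.** **1. The plan's own figure.** Inputs from Section 13: n = 40, difference 0.1, SD 0.2, alpha 0.05 (two-sided assumed). With one difference per subject, power = Φ(√40 × 0.1/0.2 − 1.96) = Φ(1.202) = 88.5%. The exact t calculation gives 86.9%. Two independent groups would give 60.9% (40 each) or 35.2% (20 each). The 89% is therefore a subject-level calculation.

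**2. Rows per subject.** Events: 10 + 5 × (5 to 7) = 35 to 45, or 1,400-1,800 for 40 subjects. Averages: 1 + (5 to 7) = 6 to 8, or 240-320. Only events can exceed 30 per subject, yet the text also says the values are averaged.

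**3. A case that can be done by hand: event rows, 6 levels for everyone.** Scale level from 0 to 1: 10 rows at 0 and 5 rows at each of 1/6, ..., 1. The mean is 0.4375 and the mean square 0.316, so the sum of squares per subject is 40 × (0.316 − 0.4375²) = 4.98. Let ω be the SD of PAT level between subjects, τ the SD of slope over the full range, and σ the SD of a single event. Because all subjects share the same levels, the pooled slope equals the mean of the subject slopes. Then:

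- true variance = (τ² + σ²/4.98)/40
- reported variance ≈ (ω² + 0.316τ² + σ²)/(40 × 4.98)
- null rejection ≈ 2[1 − Φ(1.96 × reported SE/true SE)]

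| ω / τ / σ (assumed) | True SE | Reported SE | Ratio | Rejection, formula | Rejection, simulated |
|---|---|---|---|---|---|
| 0.2 / 0 / 0.1 | 0.0071 | 0.0158 | 2.24 | 0.0% | 0.0% |
| 0.2 / 0 / 0.2 | 0.0142 | 0.0200 | 1.41 | 0.6% | 0.7% |
| 0.2 / 0.1 / 0.2 | 0.0212 | 0.0204 | 0.96 | 5.9% | 6.6% |
| 0.2 / 0.2 / 0.2 | 0.0347 | 0.0216 | 0.62 | 22.3% | 22.1% |
| 0.1 / 0.2 / 0.1 | 0.0324 | 0.0128 | 0.39 | 43.9% | 44.8% |

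**4. Wider range by simulation.** Settings: 3,000 trials each, 40 subjects, level entered as step number, ω 0.1-0.2, τ 0-0.2, σ 0.1-0.2, no mean effect, nominal 5%.

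| Rows pooled | Levels | Rejection, τ 0-0.05 | Rejection, τ 0.1-0.2 |
|---|---|---|---|
| Events | 5-7, varying | 5-16% | 15-52% |
| Events | 6 for all | 0-7% | 7-45% |
| Averages | 5-7, varying | 0-2% | 0-16% |
| Averages | 6 for all | 0-1% | 0-8% |

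The one-sample t-test on subject slopes rejected in 4.1-6.1% over all null settings.

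**5. Power for a mean change of 0.1, averaged rows, τ 0.1-0.2.** With ω = 0.2, the pooled regression has 58-91% against 78-100% for the slope t-test. With ω = 0.1 there is no material loss (81-100% against 78-100%).

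**The case against.** The wording neither names nor excludes a subject term. It follows directly after the per-subject regressions, so combining the subject slopes may have been intended. That is possible, but the text does not say so, and running the same kind of regression on combined values most naturally means raw pooling. Section 13 needs the same edit either way.

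Some settings come out near 5%, for example 5.4% for events with varying levels at ω/τ/σ = 0.1/0/0.2. That is true, but it is opposing errors cancelling, and the plan gives no basis for expecting it.

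The plan's SD of 0.2 could narrow the range. If it is the SD of the difference between a 10-event baseline and a 5-event top level, then τ = √(0.04 − 0.3σ²), where 0.3 = 1/10 + 1/5. This gives 0.19 at σ = 0.1 and 0.17 at σ = 0.2. The formula in step 3 then gives about 17% (ω = σ = 0.2) to 43% (ω = σ = 0.1) for event rows, which is too liberal throughout. This stands as a conditional point: under that reading the direction is fixed for event rows. It stays open for averages, where the simulated range at τ = 0.2 is 1.3-15.6%. The plan does not say what the SD describes.

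The subject-level test does not automatically inherit the 89%. This stands, and the fix takes it up.

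Finally, the study is small, unrandomised and mechanistic, and no interim decision depends on the test. That limits the consequences but leaves the primary outcome without another cohort-level analysis.

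**Conclusion.** The concern holds. Followed as written, Section 13 gives the primary outcome a cohort-level test whose standard error does not estimate its true uncertainty. Across the assumed settings the reported standard error runs from about one third of the true one (0.33, events with varying levels) to almost five times it (4.92, averages with 6 levels for all). It would be wrong to say that pooling always inflates false positives.

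The percentages rest on assumed variance components, on step-number coding and on complete data (10 baseline events and 5 per level for every subject). The conclusion rests on none of them singly. It rests on the absence of a valid stated cohort-level analysis for the primary outcome, which should be corrected before the data are analysed.

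**What to change.** In Section 13, replace the pooled regression with one pre-stated analysis that keeps the subject as the unit:

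- **Simplest choice:** a one-sample t-test on the per-subject slopes already planned.
- **Alternative:** a linear mixed model with random intercept and random slope by subject, and level centred within subject. This model was not simulated here.
- **Definitions:** state whether rows are events or level averages, how level is coded, and whether the number of levels may differ between subjects.
- **Reporting:** give the mean within-subject slope with its 95% confidence interval as the Aim 1 result.
- **Power:** say which subject-level comparison the 89% refers to and what the SD of 0.2 describes. State power separately for the slope test.

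The cost is three or four sentences, with no extra data or visits. Reported precision may be less favourable than under event-level pooling. The change does not itself require more subjects, but whether 40 give the intended power depends on the slope SD. For a mean change of 0.1 with averaged rows and ω = 0.2, the slope test has 99-100% power at slope SD 0.1 and 78-86% at 0.2.
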